11.2.4 Safety Analysis Set

The Safety Analysis Set comprises all subjects in the ITT Analysis Set who receive any amount of IP (CSL312 + SOC or placebo + SOC), and will be based on the actual treatment received.

11.2.5 Pharmacokinetic Analysis Set

The PK Analysis Set will comprise all subjects in the Safety Analysis Set who received any amount of CSL312 + SOC and have ≥ 1 blood sample available after administration of CSL312 for CSL312 concentration measurement. PK analyses will not be performed for subjects who are treated with placebo + SOC.

11.2.6 CCI [REDACTED]

CCI [REDACTED]
[REDACTED]
[REDACTED]

11.3 Analyses of Primary Efficacy

The primary endpoint for this study is the incidence of tracheal intubation or death prior to tracheal intubation from randomization to Day 28. The proportion will be calculated as the number of subjects with tracheal intubation or death divided by the total number of subjects for each treatment group. Treatment effect of interest (ie, estimand) is defined as the proportion difference of tracheal intubation or death prior to tracheal intubation (CSL312 + SOC minus placebo + SOC) in the target population regardless of whether additional treatment is used or initial SOC has changed. The ITT Analysis Set will be used for the primary efficacy analyses.

Firth logistic regression model including treatment group; age group as a continuous covariate; gender (male or female); country (USA or Brazil); and Baseline comorbidities (yes or no) as categorical covariates will be used to compare the rates between the 2 treatment groups. Comorbidities include hypertension, diabetes, and obesity (defined as body mass index ≥ 30 [kg/m²]). A 2-sided p-value will be estimated from the model. The proportion difference and associated 95% confidence interval (CI) will be estimated using the method described by Ge et al [2011]. The mITT Analysis Set will be used for primary efficacy endpoint sensitivity analysis.

Sensitivity analyses to assess the effect of missing data will be conducted, for example, by performing tipping point analyses that vary assumptions about the missing outcomes in both study treatment groups.

11.4 Analyses of Secondary Efficacy

The following secondary efficacy endpoints will be summarized by treatment group using subject count and percentage:

- All-cause mortality
- Incidence of tracheal intubation from randomization to Day 28

- Proportions of subjects using CPAP or BiPAP
- Proportion of subjects using HFNC
- Proportion of subjects using ECMO

The same testing method used for the primary efficacy variable will also be used to compare the above secondary efficacy endpoints between the 2 treatment groups. The proportion differences, associated 95% CIs, and 2-sided p-values will be reported.

Clinical Status Assessed on an 8-Point NIAID Ordinal Scale

Frequency and proportion of subjects within each category of the 8-point NIAID ordinal scale will be summarized along with graphical displays for each treatment group. Frequency and proportion of subjects with an improvement from Baseline of ≥ 2 points will be analyzed using descriptive statistics.

Hospital Length of Stay

Hospital LOS is defined as the time interval from randomization to hospital discharge alive. In this analysis, for subjects who did not have hospital discharge (ie, no recorded date of hospital discharge) and did not die, the time to hospital discharge will be censored at the last known in-hospital date if the subject did not complete the 28-day Treatment Period. For subjects who do not have a hospital discharge event or censoring time within the 28 days after randomization or for subjects who have died, an administrative censoring will be applied at 28 days.

Hospital LOS will be analyzed using Cox model including treatment group; age as a continuous covariate; gender (male or female), country (USA or Brazil); and comorbidities (yes or no) as categorical covariates in the model. Hazard ratio, its 95% CI and 2-sided Wald p-value for hypothesis-testing will be estimated from the model. Cumulative event rates will be calculated using the Kaplan-Meier (KM) method. The effect over time will be illustrated with a plot of the complement ($1 - KM$) of KM estimates. Event counts and percentages will be summarized. If ties occur, Efron's method will be used to adjust for ties.

Sequential Organ Failure Assessment

Maximum SOFA score, maximum change from Baseline in SOFA score, and mean SOFA score during the study will be calculated for each subject and summarized by treatment group. Descriptive statistics for continuous variables will be reported. Median differences between treatment groups and 95% CIs using Hodges-Lehmann's method will be reported. Nonparametric Wilcoxon rank-sum test will be used to compare the 2 treatment groups. SOFA score components will also be summarized by treatment and visit using descriptive statistics.

The ITT Analysis Set and mITT Analysis Set will be used for the secondary efficacy endpoint analyses.

Baseline is defined as the most recent, non-missing value before randomization, if applicable, otherwise, the most recent non-missing value before administration of IP.

11.5 Analysis of Safety

Adverse events will be coded using the Medical Dictionary for Regulatory Activities (MedDRA) version 21.1 (or higher). A treatment-emergent adverse event (TEAE) is defined as an AE reported at or after the start of the first administration of study treatment. Only TEAEs will be summarized.

An overview summary of TEAEs, including counts and percentages of subjects with any TEAE; TEAEs related to study treatment; TEAEs leading to permanent discontinuation of study treatment; TEAE leading to dose modifications; serious TEAEs; serious TEAEs related to study treatment; fatal TEAEs; fatal TEAEs related to study treatment, TEAEs by severity, and TEAEs of special interest will be produced.

TEAEs will be summarized by system organ class and preferred term. TEAEs will also be summarized by causality and severity. All TEAE summaries will be provided for each treatment and overall.

Number and percentage of subjects with plasma anti-CSL312 antibodies will be summarized by treatment group and overall.

Laboratory evaluations (hematology, biochemistry, and urinalysis) will be summarized descriptively by treatment group.

Vital sign findings and respiratory parameters will be listed by subject and time point. The values and change from Baseline at each visit will be descriptively summarized by treatment group.

The Safety Analysis Set will be used for all safety analyses.

11.6 Analyses of Pharmacokinetics

The PK data for CSL312 plasma concentration will be summarized by nominal time point for each treatment group. The following descriptive statistics will be presented for plasma concentration summaries: n, arithmetic mean, SD, CV%, median, geometric mean, minimum, and maximum.

The PK parameters for CSL312, derived using a noncompartmental method, will be summarized descriptively by treatment group.

The following PK parameters will be derived and summarized:

- C_{max}
- AUC_{0-last}
- T_{max}
- $T_{1/2}$

The following descriptive statistics will be presented for all PK parameters, except for T_{max} , n, arithmetic mean, SD, CV%, median, geometric mean, minimum, and maximum. For T_{max} , n, median, minimum and maximum will be summarized.

The PK Analysis Set will be used for all PK analyses.

11.7 CCI

CCI

CCI

CCI

11.8 Interim Analysis

An interim analysis of unblinded primary endpoint data is planned after 62 subjects (50% of the target sample size) have completed primary endpoint assessment. The interim analysis will be performed for the purpose of futility monitoring and sample size re-estimation.

At the interim analysis, the conditional power (CP) will be calculated assuming the data yet to be observed follow the current trend observed in the data available for the interim analysis. Chen et al [2004] showed that stopping a study early for futility or increasing the sample size when the interim result is promising will not inflate the Type I error rate. Thus, a statistical adjustment for multiplicity is not necessary to control the overall Type I error of the study. Mehta and Pocock [2011] have shown that the boundary for the promising interim result may be lowered to 0.36, if the maximum allowable sample size is restricted to 2 times the original sample size.

Based on the review of the interim analysis, early stopping for futility or sample size re-estimation may be recommended for implementation following these guidelines:

- Stop for futility if $CP < 0.10$ (futility zone)
- Continue to the planned completion if $0.10 \leq CP < 0.36$ (unfavorable zone)
- Increase the sample size up to 200 if $0.36 \leq CP < 0.80$ (promising zone)
- Continue to the planned completion if $CP \geq 0.80$ (favorable zone)

Full details of the interim analysis, including the formula to calculate the CP will be specified in the IDMC statistical analysis plan. Although the statistical guidelines will be pre-specified, a number of factors must be considered thoroughly as part of the decision to modify or stop the study early. A recommendation to modify or terminate the study will not be based solely on statistical grounds.

12 Regulatory and Ethics Considerations

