- Change in Sequential Organ Failure Assessment (SOFA) score
- Length of hospital stay
- Subjects experiencing the following safety events:
 - Adverse events (AEs)
 - Serious adverse events
 - Adverse events of special interest
 - CSL312-induced anti-drug antibodies
 - Clinically significant abnormalities in laboratory assessments reported as AEs
- CSL312 PK in plasma:
 - Maximum plasma concentration (C_{max})
 - Time to maximum plasma concentration (T_{max})
 - Area under the plasma concentration-time curve from time zero to the time of the last measurable concentration (AUC_{0-last})
 - Terminal half-life ($T_{1/2}$)

Study Duration

The duration of an individual subject's study participation is expected to be up to 30 days. This estimate is based on:

- A Screening Period of up to 2 days.
- A Treatment Period of up to 28 days.

The overall study duration (ie, first subject's Screening Visit to last subject's last study visit) will be approximately 6 months.

Number of Subjects

This study will enroll a total of approximately 124 subjects; 62 subjects in the CSL312 + SOC group and 62 subjects in the placebo + SOC group.

After the first 62 subjects have completed the primary endpoint assessment, an interim analysis will be performed for futility monitoring and sample size re-estimation, which may result in an increase in the target sample size.

**Study Population
and Main Criteria
for Eligibility**

Inclusion criteria:

1. Capable of providing written informed consent. An individual legally permitted to make medical decisions on the subject's behalf can provide written informed consent.
2. Willing and able to adhere to all protocol requirements
3. Age \geq 18 years at the time that informed consent is obtained
4. Positive for severe acute respiratory syndrome coronavirus-2 (SARS-CoV-2) infection as determined using a molecular diagnostic test (reverse transcription polymerase chain reaction [RT-PCR] or equivalent) approved by regulatory authorities (including Food and Drug Administration or Brazilian Health Regulatory Agency) or allowed under an emergency use authorization within 14 days before Screening. If a false negative result is suspected, the SARS-CoV-2 test may be repeated within the Screening Period.
5. Chest computed tomography (CT) scan or X-ray results confirming interstitial pneumonia
6. Severe COVID-19 disease as evidenced by \geq 1 of the following criteria at Screening including within 24 hours before Screening:

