3.1 Planned Number of Subjects

This study will enroll a total of approximately 124 subjects; 62 subjects in the CSL312 + SOC group and 62 subjects in the placebo + SOC group.

After the first 62 subjects have completed the primary endpoint assessment, an interim analysis will be performed for futility monitoring and sample size re-estimation, which may result in an increase in the target sample size of up to 248 subjects. Additional details on the interim analysis are provided in [Section 11.8](#).

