## 4.4 Determination of the Initial Sample Size

There are limited data on the rates of subjects with COVID-19 who progress to tracheal intubation or death prior to tracheal intubation within 28 days. For sample size calculation, a rate of 30% in the control group and a rate of 10% in the CSL312 group have been assumed. With a 1-sided  $\alpha = 0.025$  (which is equivalent to a 2-sided  $\alpha = 0.05$ ) and 1:1 randomization ratio for CSL312 + SOC versus placebo + SOC, a total of 124 subjects need to be randomized (62 subjects to CSL312 + SOC and 62 subjects to placebo + SOC) to achieve 80% power to show superiority using a 2 group chi-square test. For the sample size calculation, it is further confirmed using simulations performed in East 6.5 that 80% power is maintained, accounting for the interim analysis for futility and sample size re-estimation.

Depending on the results after the interim analysis, the sample size may be increased up to 248 subjects (124 subjects in CSL312 + SOC and 124 subjects in placebo + SOC).

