## 5 Changes from the Protocol Planned Analyses

There are no changes to the analyses planned as specified in the study protocol.

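### The maximum sample size after the interim analysis is 200 in Protocol 11.8 but 248 in Protocol 3.1, SAP 4 and SAP 4.4

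*Protocol*

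**What the plan says.** Four places in the current text give a maximum for the interim re-estimation.

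- **Protocol 11.8**, promising zone (conditional power from 0.36 to below 0.80): "Increase the sample size up to 200 if" that condition is met.
- **Protocol 3.1**: an interim analysis "which may result in an increase in the target sample size of up to 248 subjects". The same paragraph points to 11.8: "Additional details on the interim analysis are provided in" that section.
- **SAP 4**: the same figure of 248.
- **SAP 4.4**: "the sample size may be increased up to 248 subjects (124 subjects in CSL312 + SOC and 124 subjects in placebo + SOC".

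The related text does not settle the matter:

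- SAP 5 states: "There are no changes to the analyses planned as specified in the study protocol".
- The Protocol Synopsis says only "which may result in an increase in the target sample size", with no cap.
- Protocol 11.8 ties its 0.36 bound to a condition, "if the maximum allowable sample size is restricted to 2 times the original sample size", and defers the rest: "Full details of the interim analysis, including the formula to calculate the CP will be specified in the IDMC statistical analysis plan". SAP 4.5.2 also defers to the IDMC SAP (version 1.0, 28 Aug 2020, per SAP 3), which is not among the documents available here.

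**The concern.** One re-estimation has two maxima. Protocol 3.1 sends the reader to 11.8 for detail and the reader finds a different number there. The per-arm split in SAP 4.4 shows that 248 is a total and not a number of added subjects. The 200 cannot be per arm, because 400 would exceed every other figure and the limit of twice the original size.

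The maximum is a pre-specified decision figure in a design that uses unblinded efficacy data. Enrolling subject 201 would follow Protocol 3.1 and the SAP but not Protocol 11.8. If the cap were settled only after unblinded results had been reviewed, the choice could look data-driven, and no later analysis could remove that doubt. In addition, Protocol 11.1 and SAP 4.4 rest the 80% power claim on simulations that include the re-estimation, without naming the cap simulated.

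**Working it through.** **Inputs.** Event rates 30% and 10%, 80% power, two-sided 0.05 (one-sided 0.025 in the SAP), 1:1 allocation, chi-square test, N = 124 (Protocol 11.1, SAP 4.4). Interim at 62 subjects, conditional power under the current trend, zone bounds 0.10, 0.36 and 0.80 (Protocol 11.8). Caps 200 and 248 as quoted.

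**1. The plan's own sample size.** Pooled variance, no continuity correction:

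n per arm = [1.96·√(2·0.2·0.8) + 0.8416·√(0.3·0.7 + 0.1·0.9)]² / 0.2² = 61.6, so 62 per arm and 124 in total, with power 0.803. The base figure reproduces.

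**2. The two caps against the base.**

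| Cap | Ratio to 124 | Added subjects | Increase |
|---|---|---|---|
| 200 | 1.61 | 76 | 61% |
| 248 | 2.00 | 124 | 100% |

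The gap is 248 − 200 = 48, or 24 per arm. Both meet the limit of twice the original size: 248 equals it and 200 lies inside it. Neither number is a miscalculation; they simply disagree.

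**3. A case where the caps give different answers.** The sponsor's conditional power formula is not in the visible documents, so I used the standard current-trend form, with z₁ the pooled interim statistic:

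CP(N) = Φ{[z₁√62 + z₁(N − 62)/√62 − 1.96√N] / √(N − 62)}

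The bounds 0.10, 0.36 and 0.80 fall at z₁ = 0.745, 1.207 and 1.807. Assume 31 per arm, with 7 placebo and 3 CSL312 events:

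- z₁ = (7/31 − 3/31) / √[(10/62)(52/62)(2/31)] = 1.381
- CP(124) = 0.496, which is in the promising zone
- CP(200) = 0.735 and CP(248) = 0.823
- CP reaches 0.80 at N = 233.7, so 234 subjects

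Protocol 3.1 and the SAP allow 234. Protocol 11.8 does not.

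**4. How often it matters.** Exact binomial probabilities at 30% and 10%, 31 per arm: futility 9.8%, unfavorable 9.8%, promising 22.2%, favorable 58.3%. If the rule is to go to the cap, the two caps give different sizes in all of the 22.2%. If the rule is to go only as far as 80% conditional power, they differ in 8.0% of trials. The visible documents do not say which rule applies.

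**5. Operating characteristics.** Normal integration over z₁, unadjusted critical value 1.96; power and mean N are with futility stopping:

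| | Cap 200 | Cap 248 |
|---|---|---|
| One-sided error (range over both rules, binding and non-binding futility) | 0.0212–0.0244 | 0.0207–0.0243 |
| Power, increase to cap | 80.0% | 80.7% |
| Power, increase to 80% CP | 79.2% | 79.5% |
| Mean N, increase to cap | 133 | 144 |
| Mean N, increase to 80% CP | 128 | 131 |

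**6. Side check on the 0.36 bound.** The final critical value that preserves the conditional error is b = [√((N − 62)/62)·(1.96√124 − z₁√62) + z₁√62]/√N. Setting b = 1.96 gives a lowest supporting conditional power of 0.358 for N = 248 and 0.393 for N = 200. This is my own calculation, not a figure in the documents.

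**The case against.** The strongest reply is that little depends on the difference. Estimand, endpoint, test and critical value are untouched, and about 78% of trials at the design rates would never reach the promising zone. Both statements are upper bounds, so an increase to 200 or fewer satisfies every text. Because 3.1 refers to 11.8, the tighter figure could be read as the operating rule. Protocol 11.8 also calls its zones guidelines and says a recommendation will not rest on statistics alone. The IDMC works from its own SAP, which may name one cap clearly. Finally, 200 may be a slip for 200%, which would be 248.

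Part of this stands. The statistical cost is small, *inconsistent* describes the defect better than *miscalculated*, and what the IDMC itself has been told cannot be checked here. The figures beyond the simple comparison also rest on a pooled z statistic and an equal interim split, whereas the final test is a Firth logistic model; uneven splits from 29/33 to 33/29 move the promising-zone share to between about 20% and 23%.

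The rest does not remove the problem. Reading 11.8 as overriding leaves the specific 124 per arm in SAP 4.4 unexplained. Discretion over whether to increase does not say how far an increase may go. Whichever cap the IDMC SAP names, it will disagree with either 3.1 or 11.8. The percent-sign explanation is a guess: another percent sign in the same section is intact.

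**Conclusion.** The concern holds. The protocol contradicts itself, and the SAP agrees with one of its two figures while declaring no change. The SAP is based on Amendment 2, and the Amendment 3 entry lists only contraception and thermometer changes, so the amendment history does not explain the gap.

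Its size is 48 subjects in the maximum, relevant in roughly 8% to 22% of trials at the design rates depending on the re-estimation rule. Those percentages assume 31 per arm at the interim and the conditional power formula above; the contradiction itself needs no assumption. This is not a finding of inflated error or lost power. It must be fixed because a decision figure of an unblinded adaptive design has to be a single number before the interim data are seen. Confidence is high.

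**What to change.** Before the interim analysis, state one cap in Protocol 3.1, Protocol 11.8, SAP 4 and SAP 4.4, and confirm that the IDMC SAP gives the same figure.

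- **If 248 is intended**, one number changes, in Protocol 11.8. This is the smallest edit and equals the limit of twice the original size cited there. It permits up to 48 more subjects than 11.8 does now, but no more than 3.1 and the SAP already allow.
- **If 200 is intended**, change Protocol 3.1, SAP 4 and SAP 4.4 (100 per arm). The sponsor may then also wish to raise the 0.36 bound to about 0.40 in light of the side check, but overall error control does not require it.

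In either case, say in Protocol 11.1 and SAP 4.4 which cap the power simulations used; no rerun is requested. The cost is a short amendment with IRB/IEC approval under Protocol 13.3, a SAP edit if 200 is chosen or to name the simulated cap, and a check of the IDMC SAP. The analysis is unchanged.

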12.1 Regulatory Considerations

CSL or its agents will submit the appropriate documents to the local regulatory agencies and will await approval before commencement of the study.

This study will be conducted and documented in accordance with the applicable regulatory guidelines and requirements.

The procedures set out in this CSP are designed to ensure that CSL and the investigator abide by the principles of the current ICH GCP guidelines on the conduct, evaluation, and documentation of this study, as described in ICH E6 (Guideline for GCP). The study will also be carried out according to all applicable international and national regulatory requirements.

12.2 Institutional Review Board/Independent Ethics Committee

The investigator must submit the CSP and informed consent forms (ICFs) for review by an authorized and properly constituted (according to local guidelines) IRB/IEC. Written approval must be received from the IRB/IEC before commencement of the study.

12.3 Subject Information and Informed Consent

Informed consent of study subjects according to the standards of GCP must be implemented in this clinical study before protocol-specified procedures are carried out. Information should be given in both oral and written form and should be deemed appropriate by the IRB/IEC. Subjects, their relatives (or if necessary, legally acceptable representatives) must be given ample opportunity to inquire about the details of the study.

The subject (or if necessary, legally acceptable representatives) must be provided with a copy of the signed ICF.

Should there be any amendments to the CSP that would directly affect the subject's participation in the study (eg, a change in any procedures), then the ICF must be amended to incorporate this modification. Subjects must be informed of the change and they must sign the amended ICF indicating that they re-consent to participate in the study.

12.4 Subject Confidentiality

All subject names and contact details will be kept confidential. Subjects will be identified throughout documentation and evaluation by the subject number assigned to them during the study. Each subject will be told that all study findings will be handled in the strictest confidence.

The investigator at the study site will be responsible for retaining sufficient information about each subject (eg, name, address, phone number, and identity in the study) so that regulatory agencies or CSL may access this information should the need arise. These records should be retained in a confidential manner as long as legally mandated according to local requirements.

Subject medical records pertaining to the study may be inspected/audited at any time by CSL employees or their duly authorized representatives, a health authority or the IRB/IEC. All records accessed will be strictly confidential. Consent to participate in the study includes consent to these inspections/audits

